4.8 Exposure and Treatment Compliance

All exposure summaries are to be presented for the Safety analysis set for Part 1 and Part 2.

Exposure to study drug and reasons for discontinuation will be tabulated. The number of treatment cycles received along with the duration of treatment exposure, dose interval (the days between two consecutive dosing dates), average dose intensity (sum of the dose intensity (mg/kg) received in all cycles divided by the number of cycles), and relative dose intensity (total actual dose / total planned dose) will be summarized.

Summaries will be provided for doses intensity of study drug (mg/kg) and relative dose intensity by cycle.

Descriptive summaries will be provided for dose changes. Reasons for dose changes will be summarized across the study, for each of the following changes: cycle delay (>3 days), dose reduction, and infusion interruption/rate change. Adverse events leading to each type of dose change will be summarized. Summary of time to the first infusion or dose modification (dose reduction, infusion interruption/abortion/rate change, or cycle delay) from the first dose date will also be provided.

A summary table of the duration of the study follow-up will be produced and a by-subject listing of treatment compliance data and a by-subject listing of exposure data will also be provided.

4.9 Efficacy Evaluation

4.9.1 Analysis and Data Conventions

Unless otherwise specified, all statistical tests will be interpreted at a 2-sided nominal significance level of 0.05 and all CIs at a 2-sided level of 95%. The overall type I error rate is 0.05 (two-sided) for the primary and secondary efficacy hypotheses in each part of the study.

Statistical Hypotheses for Trial Objectives

For Part 1 (Phase 2), RBC TI in 5 or more of 30 subjects rejects null rate of 6.5% with a single-arm, one-sided, level 0.05 exact test.

For Part 2 (Phase 3), the primary hypothesis of this study is that the imetelstat will significantly improve the rate of RBC TI as compared to placebo in transfusion dependent subjects with low or intermediate-1 risk MDS that is relapsed or refractory to ESA treatment.

The statistical hypotheses are as follows:

H₀: The RBC TI rate of experimental treatment group and the placebo group are equal.
H₁: The RBC TI rate of experimental treatment group is greater than the placebo group.

The hypothesis will be tested using a stratified Cochran-Mantel-Haenszel (CMH) test adjusting for the stratification factors at a two-sided significant level of 0.05.

4.9.1.1 Handling of Missing Data

No imputations for missing data will be made for the primary and secondary efficacy endpoints. The double-blind study design of Part 2 and the symmetric assessment schedule reduce the potential for systematic bias, but the treatment effect may be attenuated by missing transfusion data. In order to be considered transfusion independent, a subject must have completed continuous transfusion assessments throughout the qualifying observation period where his/her transfusion independence is determined. An apparent transfusion free period with one or more missing transfusion assessments will not be considered a qualifying 8-week or 24-week TI period. Subjects with no qualifying observation periods will be considered non-responders.

The number and percentage of subjects with missing data for the primary endpoint will also be summarized by major reason. In addition, a Kaplan-Meier plot of the time to study discontinuation will be provided.

A subject data listing will be provided showing all subjects with missing values for the primary endpoint. For these subjects, the listing will provide the observed data relating to the primary endpoint, important baseline characteristics, the recorded reason(s) for study discontinuation and the timing of study discontinuation.

4.9.1.2 Adjustments for Covariates

For Part 2, the 8-week RBC TI rates will be summarized with frequencies and percentages along with 2-sided 95% exact Clopper-Pearson CIs for the 2 treatment groups. Difference in TI and its 95% CI will be presented using Wilson Score method [1]. The comparison will be based on a stratified CMH test adjusting for the following baseline covariates used for stratified randomization:

1. prior RBC transfusion burden (≤ 6 or > 6 units RBC)
2. IPSS risk group (low risk or intermediate-1 risk)

An ‘unadjusted’ sensitivity analysis will be performed to assess the robustness of the study results, which is detailed in section 4.9.2.3.

4.9.1.3 Multiple Comparisons/Multiplicity

Testing of Primary Endpoint for Part 2 (Phase 3)

For Part 2, the primary hypothesis is that imetelstat will increase the rate of RBC TI as compared to placebo in transfusion dependent subjects with low or intermediate-1 risk MDS that is relapsed/refractory to ESA treatment. The primary efficacy hypothesis on 8-week RBC TI will be tested at 0.05 (two-sided) for Part 2.

Testing of Secondary Endpoints for Part 2 (Phase 3)

For Part 2, a sequential gate-keeping procedure and Hochberg procedure will be implemented to ensure that the overall type I error rate for the secondary endpoints is controlled. Let α be the critical type I error rate 0.05 (2-sided). 24-week RBC TI and rate of HI-E per modified IWG 2006 are the most important secondary endpoints, thus will be used as gate keepers and be tested at the α level sequentially. 24-week RBC TI will be the first gate keeper and rate of HI-E per modified IWG 2006 will be the second gate keeper. If the nominal p-value is $< \alpha$ for 24-week TI, then rate of HI-E will be tested next at the α level. If the nominal p-value is $< \alpha$ for rate of HI-E as well, the remaining selected secondary hypotheses (PFS, and OS) will be tested using a Hochberg procedure [2].

In summary, the secondary endpoints as the gate keepers which will be tested sequentially at 0.05 (2-sided) are:

1. 24-week RBC TI
2. Rate of HI-E per modified IWG 2006

If the above two gate keepers are significant, the following endpoints will be tested using a Hochberg procedure:

- PFS
- OS

In general, Hochberg procedure is conducted as the following steps:

1. Suppose we have H_1, \dots, H_m null hypotheses tested and P_1, \dots, P_m as their corresponding p-values. We order these p-values in increasing order and denote them by $P_{(1)}, \dots, P_{(m)}$.
2. For a given significance level α , find the largest k such that $P_{(k)} \leq \alpha / (m+1-k)$.
3. Reject the null hypothesis for all $H_{(i)}$ for $i=1, \dots, k$.

Note that Hochberg procedure does not require the order of hypotheses and it controls the overall type I error when conducting multiple comparisons at the given significance level α if the p-values are independent or positively correlated.

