The distributions of OS, PFS, and time to progression to AML will be compared using a stratified log rank test for the ITT population. The Kaplan-Meier method will be used to estimate the distribution for each treatment. The treatment effect (hazard ratio) and its 2-sided 95% confidence intervals are to be estimated using a stratified Cox regression model with treatment as the sole explanatory variable. The reasons of censoring in time to progression to AML will be tabulated.

The time to 8-week and 24-week RBC TI will be summarized descriptively based on ITT 8-week and 24-week RBC TI responders, respectively. The Kaplan-Meier method will be used to estimate the distribution of duration of RBC TI based on ITT 8-week and 24-week RBC TI responders, respectively.

The amount and relative change in RBC transfusions will be summarized descriptively by treatment by time point.

Change from baseline in scores from QUALMS, FACT-An, and EQ-5D-5L will be summarized descriptively by treatment group. The PRO measure of interest and analysis methods (eg, responder analysis, longitudinal analysis with repeated measures) will be specified in the Statistical Analysis Plan.

A sequential gate-keeping procedure will be implemented to ensure that the overall type I error rate for the secondary endpoints is controlled. Details of selected secondary endpoints to be tested

and the testing procedure will be specified in the Statistical Analysis Plan.

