4.9.2.2 Analysis Methods

The primary efficacy analysis is planned at 12 months after the last subject is randomized in the main study of Part 2, and the final analysis is at the End of the Study defined as 24 months after randomization of the last subject in the main study of Part 2 or anytime the sponsor terminates the study, whichever comes first.

Efficacy data in Part 1 will be descriptively summarized based on the treated population. Efficacy data the main study of in Part 2 will be compared between the imetelstat and placebo groups based on the ITT population. Any available efficacy data from Ventricular Repolarization Substudy will be descriptively summarized in addition to the efficacy data from the main study in Part 2.

Part 1 (Phase 2):

The proportion of subjects with 8-week RBC TI will be summarized with a frequency and percentage along with its 95% 2-sided exact Clopper-Pearson CI. The forest plot of the subgroup (defined in section 4.9.1.4) corresponding rate and associated 2-sided 95% CIs will be presented.

Part 2 (Phase 3):

The 8-week RBC TI rates will be summarized with frequencies and percentages along with 2-sided 95% exact Clopper-Pearson CIs for the 2 treatment groups. Difference in TI and its 95% CI will be presented using Wilson Score method [1]. The comparison will be based on a stratified CMH test adjusting for the stratification factors at a two-sided significance level of 0.05:

1. Prior RBC transfusion burden (≤ 6 or > 6 units RBC)
2. IPSS risk group (low risk or intermediate-1 risk)

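### SAP 4.9.1.3 does not make the secondary testing chain conditional on the primary test and names no data cut for it, so the overall 0.05 stated in SAP 4.9.1 is not secured as written

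*SAP*

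**What the plan says.** **Overall claim.** SAP 4.9.1: "The overall type I error rate is 0.05 (two-sided) for the primary and secondary efficacy hypotheses in each part of the study". The alternative hypothesis there is one-directional: "The RBC TI rate of experimental treatment group is greater than the placebo group".

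**Primary test.** SAP 4.9.1.3: "The primary efficacy hypothesis on 8-week RBC TI will be tested at 0.05 (two-sided) for Part 2".

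**Secondary chain.** Under its own subheading, SAP 4.9.1.3 introduces gate-keeping plus Hochberg "to ensure that the overall type I error rate for the secondary endpoints is controlled". The order is explicit: "24-week RBC TI will be the first gate keeper and rate of HI-E per modified IWG 2006 will be the second gate keeper". HI-E is tested if 24-week TI is significant. If HI-E is significant too, "the remaining selected secondary hypotheses (PFS, and OS) will be tested using a Hochberg procedure". The closing summary of the section also begins at 24-week TI. Protocol 11.4 has the same scope ("A sequential gate-keeping procedure will be implemented to ensure that the overall type I error rate for the secondary endpoints is controlled") and leaves the details to the SAP.

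**Timing.** SAP 4.9.2.2: "The primary efficacy analysis is planned at 12 months after the last subject is randomized in the main study of Part 2"; the final analysis follows at 24 months. SAP 4.9.1.3 and 4.9.3.2 do not say which analysis carries the secondary tests. Protocol 11 adds a PFS and OS analysis at the end of the Extension Phase.

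**Unblinding.** Under Amendment 8 (Protocol 3.2 and 5.2), subjects, investigators and the study team are unblinded once the primary efficacy analysis is done, and placebo subjects may stop treatment. The SAP is written to Amendment 7. Its section 3.1 says only that subjects and investigators might be unblinded at that point, depending on the results.

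**The concern.** Every later link in the chain is written as a condition; the link from 8-week TI to 24-week TI is not. The procedure is said to control error for the secondary endpoints only, which is narrower than the joint claim in SAP 4.9.1. Two separate tests at 0.05 do not add up to an overall 0.05. In practice, a significant 24-week result after a non-significant primary would have no defined status.

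The missing data cut is a second gap, and it applies to the gate keepers as well as to PFS and OS. Responders can accrue between 12 and 24 months, so a gate failed at the first analysis could be tried again at the second. The choice of cut for PFS and OS could also be made after the 12-month results are known. The two cuts differ in kind. After unblinding, placebo subjects may move to other therapy, and SAP 4.9.3.1 censors PFS at the last assessment on or before subsequent therapy, so censoring may then differ by arm.

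**Working it through.** **Inputs from the plan.** 115 imetelstat and 55 placebo subjects; two-sided 0.05; planning rates 30% and 7.5% (SAP 4.12). The design figures reproduce. Continuity-corrected power with 100 and 50 subjects is 87.6%, against the stated 88%. Inflation for drop-out gives 150/0.90 = 167, against about 170.

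**The plan's own figure, 0.05.** With a gate, no error can be made in the chain unless 8-week TI is significant. When treatment has no effect, the overall error is therefore the size of the primary test, which simulates at about 5.0%. So 0.05 is reproduced if the gate is there.

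**Without the gate.** P(either significant) = P(8-week significant) + P(24-week significant, 8-week not). If the tests were independent this would be 1 − 0.95² = 9.75%. They are not independent, because 24-week responders are a subset of 8-week responders. I simulated nested binomial responders with equal rates in both arms, using an unstratified CMH test and 2,000,000 draws. The 24-week rates are assumptions. So are the 8-week rates, except 7.5% (planning rate), 3% (placebo rate in the earlier trial cited in Protocol 1.1.4) and 37% (Part 1 on imetelstat, 37/26%, Protocol 1.1.5). Figures are percentages; sums may differ in the last digit.

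| 8-wk / 24-wk rate | Primary, two-sided | + 24-wk only | = Either | Primary, benefit only | + 24-wk only | = Either |
|---|---|---|---|---|---|---|
| 3 / 1 | 3.45 | 2.65 | 6.10 | 0.44 | 0.00 | 0.44 |
| 7.5 / 3 | 4.97 | 2.51 | 7.47 | 2.01 | 0.31 | 2.31 |
| 7.5 / 5 | 4.97 | 2.25 | 7.22 | 1.99 | 0.87 | 2.87 |
| 15 / 5 | 5.00 | 3.30 | 8.30 | 2.17 | 1.22 | 3.39 |
| 15 / 10 | 4.97 | 2.87 | 7.84 | 2.16 | 1.22 | 3.38 |
| 30 / 10 | 5.03 | 4.06 | 9.09 | 2.36 | 1.68 | 4.05 |
| 30 / 20 | 5.01 | 2.95 | 7.96 | 2.36 | 1.35 | 3.70 |
| 37 / 26 | 4.98 | 2.95 | 7.93 | 2.37 | 1.36 | 3.73 |

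A four-stratum CMH with assumed stratum sizes, without the 3/1 and 30/10 pairs, gave 7.1 to 8.3% two-sided and 2.2 to 3.8% for benefit only. The 24-week-only columns show that nesting does not replace the gate: the 24-week test can reject when the 8-week test does not.

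**Data cut, illustration only.** The documents give no planned event counts for PFS or OS. Suppose the Hochberg step were run at both cuts at full alpha, with 50 to 90% of the final information at 12 months and a PFS–OS correlation of 0 to 0.7 (all assumed). The two-sided error would be 6.0 to 8.5%. Run once, it is 4.6 to 5.0%. With 0.025 at each cut it is 3.1 to 4.4%.

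**Deaths by each cut.** For uniform accrual over A years and exponential survival with λ = ln 2/median, D(F) = 170 × [1 − e^(−λF)(1 − e^(−λA))/(λA)], where F is years after last randomization. With median 3.5 years (Protocol 1.2), λ = 0.198; with A = 2 assumed:
- F = 1: 170 × (1 − 0.820 × 0.826) = 55
- F = 2: 170 × (1 − 0.673 × 0.826) = 76

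Loss to follow-up is ignored.

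**The case against.** The best reply is that the gate is implied. SAP 4.9.1 sets one overall 0.05, and SAP 4.9.1.3 then lists the primary first and a sequential procedure after it. A primary-first hierarchy is the reading that makes the two sections agree. That stands as a judgement of intent. A reader might infer that the sponsor means to run the chain whatever the primary shows, and so that the trial's true error is 7 to 8%. The documents do not support that; they only leave the condition unwritten.

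It is also fair that the two-sided figures count wins for placebo, while the alternative is one-directional. On false benefit the excess is small: at the planning rate the total is 2.3 to 2.9%, and at 3/1% the missing gate adds nothing. The upper values need placebo response far above the 7.5% expected.

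Two stronger readings on timing also fail. One is that PFS and OS will be tested twice at full alpha. No passage prescribes that, and Protocol 3.3 presents the Extension Phase survival data as a more precise estimate. The other is that every death after the 12-month cut falls in unblinded follow-up. Unblinding follows the primary analysis, not the cut itself, so events in between are still blinded. Nor are main-study placebo subjects described as crossing over to imetelstat, so any effect on OS is indirect.

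**Conclusion.** The point holds as a gap in the written rules. Taken literally, SAP 4.9.1.3 gives about 7 to 8% two-sided at assumed null 8-week rates of 7.5 to 37%, and 9.1% if only a third of 30% responders last 24 weeks. For false benefit against the nominal 2.5%, it gives about 2.3 to 2.9% at the planning rate and up to about 3.8% at higher assumed rates (about 4% at 30/10%). These figures rest on equal rates in both arms and on assumed 24-week rates. The order of the chain is sound once gated and tested at a single cut.

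The missing data cut is secondary. It leaves room for a later choice but does not by itself show inflation, and the two-cut rates are illustrative. The 8-week TI claim is unaffected by either gap. The point should be fixed, with high confidence in the omissions themselves.

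**What to change.** In SAP 4.9.1.3, before unblinding:

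1. State that the secondary chain is tested only if 8-week RBC TI is significant at two-sided 0.05.
2. Test the whole chain (24-week TI, HI-E, then PFS and OS by Hochberg) once, at the 12-month primary efficacy analysis. If PFS and OS are to be formally tested again at 24 months, state the alpha split; 0.025 at each cut is one that holds the level. Naming a cut for PFS and OS alone would not be enough, because the gate keepers could still be retried.
3. Label p-values from all other cuts, including the Extension Phase, as descriptive.

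This costs a few sentences and leaves sample size, primary power and conduct unchanged. The price is that no formal secondary claim is possible if the primary fails, and that the 12-month cut has fewer deaths (about 55 rather than 76 in the example above).

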4.9.1.4 Examination of Subgroups

Subgroup analyses will be performed to assess the consistency and robustness of the treatment benefit mainly for the rate of RBC TI and the rate of HI-E. Subgroup analysis may be performed for other selected efficacy and safety endpoints. CMH tests between the two treatment groups within each subgroup will be calculated for Part 2.

Note that the following subgroup variables and the cutoff values are subject to change if warranted to better represent the data.

The uniformity of the treatment effect will be examined for, but may not be limited to the following subgroups:

- Sex (male vs. female)
- Age (≤ 65 vs. > 65 years old; ≤ 75 vs. > 75 years old)
- Time since initial diagnosis (< 2 vs. ≥ 2 years)
- WHO Classification (RS+ vs. RS-)
- Prior RBC transfusion burden (≤ 6 vs. > 6 units RBC; < 8 , 8-12, or > 12 units RBC)
- Transfusion burden per IWG 2018 (HTB vs LTB)
- Baseline bone marrow blasts per central lab ($\leq 5\%$ vs. $> 5\%$)
- IPSS risk group (low risk vs. intermediate-1 risk)
- Number of cytopenia (0-1 vs. 2-3)
- Prior ESA use (yes vs. no)
- Baseline serum EPO levels (≤ 500 vs. > 500 mU/mL)
- ECOG score (0 vs. 1-2)
- IPSS-R Cytogenetic risk groups (very good/good, intermediate, or poor/very poor) [3]
- IPSS-R Prognostic risk groups (very low, low, intermediate, high, or very high) [3]
- Baseline platelets (< 150 vs. $\geq 150 \times 10^9/L$)
- Baseline neutrophils (< 1.5 vs. $\geq 1.5 \times 10^9/L$)

All factors will be based on values recorded on the eCRF as indicated above.

The corresponding rate and associated 2-sided 95% CIs will be summarized and presented on a forest plot for the 2 treatment groups of Part 2 respectively, along with the results of the overall analysis for Part 2.

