4.12 Determination of Sample Size

Approximately 270 subjects (57 subjects already enrolled in Part 1, approximately 170 subjects in the main study of Part 2, and approximately 45 subjects in Ventricular Repolarization substudy of Part 2) will be enrolled in the study.

On the basis of historical data, RBC TI rate is expected to be approximately 7.5% [15, 16] in subjects with low or intermediate-1 risk MDS without any active treatment. The RBC TI rate with imetelstat treatment is expected to be approximately 30% based on preliminary data from [17]. The futility criteria before Amendment 2 were defined as follows: If 4 or fewer subjects among 30 subjects in Part 1 achieve RBC TI lasting at least 8 weeks, the study will be stopped unless there is compelling clinical evidence of efficacy in one or more other endpoints (eg, transfusion reduction, erythroid improvement). The initial cohort of 32 subjects enrolled into Part 1 was expanded with Amendment 2 to include an additional 25 subjects with non-del(5q) MDS and without prior exposure to either hypomethylating agents or lenalidomide who meet the revised entrance criteria, for a total of 57 subjects in Part 1.

Since data from Part 1 for this target population show clinical benefit of treatment with imetelstat, Part 2 of the study will be initiated. If the RBC TI rate of 30% with imetelstat treatment is true, the probability of passing the futility criterion is 97%. All available data will be used to support the decision.

In the main study of Part 2, approximately 170 subjects will be randomized in a 2:1 ratio to receive either imetelstat or placebo the main study of Part 2. Using a 2:1 ratio randomization and a 2-group continuity corrected Chi square test with 0.05 (2-sided) significance level, 150 subjects are needed to achieve a power of approximately 88% to detect the difference between an RBC TI rate of 30% in the imetelstat group and an RBC TI rate of 7.5% in the placebo group. After correction for a 10% drop-out rate, a total of approximately 170 subjects (115 in imetelstat group and 55 in placebo group) will be needed. The overall study power from Part 1 and the main study of Part 2 is approximately 85%.

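### SAP 4.9.1.4 sets out to examine uniformity of effect but plans only separate within-level CMH tests: no interaction test, no treatment difference per level, and no date for fixing cut-offs

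*SAP*

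**What the plan says.** SAP section 4.9.1.4 gives the purpose first: "Subgroup analyses will be performed to assess the consistency and robustness of the treatment benefit mainly for the rate of RBC TI and the rate" (the second rate being HI-E). It introduces the list with "The uniformity of the treatment effect will be examined for, but may not be limited to the following subgroups". The planned test is "CMH tests between the two treatment groups within each subgroup will be calculated for Part 2". SAP section 4.9.1 sets the default threshold: "all statistical tests will be interpreted at a 2-sided nominal significance level of 0.05".

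The list and its cut points are left open: "Note that the following subgroup variables and the cutoff values are subject to change if warranted to better represent the data". No date is attached to that permission.

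The section also plans a forest plot of response rates with 95% CIs, shown for each of the two arms beside the overall result. It does not ask for the treatment difference within a level. SAP sections 4.9.1.2 and 4.9.2.2 do plan a difference with a Wilson-score CI, but only for the whole population.

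Neither document names an interaction or homogeneity test. Protocol section 11.1 leaves subgroup detail to the SAP.

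**The concern.** A claim of uniform effect is a claim about the difference between levels. A CMH test inside one level addresses only whether that level shows an effect. Its p-value depends heavily on the size of the level, so two levels with the same true effect can easily fall on opposite sides of 0.05. The only inferential output planned under a uniformity heading therefore does not match the question, and it invites the reading that a non-significant level is one where the drug does not work.

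The open cut-offs add to this. SAP section 4.5 requires decisions on excluding subjects or data from analyses to be made and documented before Part 2 is unblinded. Section 4.9.1.4 has no such safeguard, so a change made after seeing results could not be told apart from a planned one.

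What is at stake is how the subgroup tables and the forest plot will be read, not the success of the trial.

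**Working it through.** **Inputs.** Response rates 30% and 7.5%, 2:1 allocation, 150 subjects before and about 170 (115 versus 55) after drop-out, all from SAP section 4.12. Two-sided 0.05 from SAP section 4.9.1. Subgroup sizes are not given, so the split is an assumption and is varied below.

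**The plan's own figure.** SAP section 4.12 says "150 subjects are needed to achieve a power of approximately 88% to detect the difference between an RBC TI rate of 30% in the imetelstat" arm; the placebo rate is 7.5%. For 100 versus 50, the normal approximation gives 92.1% uncorrected. Subtracting 0.5(1/100 + 1/50) from the difference as a continuity correction gives 87.6%. The stated 88% is reproduced.

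**Number of levels.** In the order listed: 2 + 4 + 2 + 2 + 5 + 2 + 2 + 2 + 2 + 2 + 2 + 2 + 3 + 5 + 2 + 2 = 41 levels from 16 factors. Age and prior transfusion burden are each cut two ways, which makes 18 partitions. Not every level will be populated: inclusion criterion 8.1 requires ANC of at least 1.5 x 10^9/L, so the level with baseline neutrophils below 1.5 should be nearly empty.

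**One evenly split factor, same true effect in both halves.** Each half has about 57 versus 28 subjects. Exact enumeration of the two binomials, without further stratification inside the level, gives power p per half:

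- uncorrected: p = 0.687
- continuity-corrected: p = 0.565

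The chance that exactly one half is significant is 2p(1 - p):

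- uncorrected: 2 x 0.687 x 0.313 = 0.43
- corrected: 2 x 0.565 x 0.435 = 0.49

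**Uneven splits.** With power pA and pB in the two levels, the chance is pA(1 - pB) + pB(1 - pA).

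| Split | Level A (imetelstat vs placebo) | Level B | Uncorrected: pA, pB, chance | Corrected: pA, pB, chance |
|---|---|---|---|---|
| 40:60 | 46 vs 22 | 69 vs 33 | 0.564, 0.795, 46% | 0.398, 0.692, 54% |
| 30:70 | 34 vs 17 | 81 vs 38 | 0.437, 0.841, 54% | 0.242, 0.764, 64% |
| 20:80 | 23 vs 11 | 92 vs 44 | 0.284, 0.900, 67% | 0.106, 0.838, 77% |

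**What an interaction test would do.** Its nominal false-signal rate is 5% per factor. In simulation at 115 versus 55 with a uniform effect, a risk-difference interaction test rejected in about 3-4% of trials. A log-odds-ratio version rejected in about 1-2.5%; it is conservative because an evenly split level expects only 28 x 0.075 = 2.1 placebo responders. Over 18 partitions treated as independent, the nominal chance of at least one false signal is 1 - 0.95^18 = 60%.

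**The case against.** The SAP nowhere says that significance in one level and not in another counts as inconsistency. It sets no decision rule, and it plans a forest plot beside the tests. This stands: the 43-49% is conditional on a reader using the p-values that way. The plot is only a partial answer, because it shows rates per arm rather than treatment differences.

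The subgroup tests lie outside the type I error hierarchy in SAP section 4.9.1.3, which covers the primary endpoint, 24-week TI, HI-E, PFS and OS. This also stands. A reader might infer that the primary result is at risk; it is not.

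The count of 41 is a count of listed levels, not of usable tests. Some will be sparse, and others overlap, since transfusion burden appears in three partitions. A reader might also attach the 43-49% to the whole set of 41. It belongs to one evenly split factor. Treating all 18 partitions as independent, simulation shows at least one discordant split in almost every trial, but the overlap means the documents do not support independence, so no set-wide rate is claimed here.

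On cut-offs, a reader might infer that they will be tuned to the outcome. The text does not say that. Merging sparse levels is an equally natural meaning, and the SAP revision history shows subgroup cut-offs being clarified in a dated version (1.3). The gap is the missing deadline.

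Finally, interaction tests here would have low power and their own multiplicity. That is true, and it determines how they must be labelled.

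**Conclusion.** The concern holds in a limited form. SAP section 4.9.1.4 states a question about uniformity and plans no analysis that tests or estimates it. Under a uniform 30% versus 7.5% effect with 115 versus 55 subjects, separate within-level tests would split an evenly divided two-level factor into one significant and one non-significant level in about 43-49% of trials, and in about 46-77% for splits from 40:60 to 20:80. These figures rest on the planned response rates, on assumed subgroup sizes, on unstratified tests inside each level, and on the p-values being read as evidence about uniformity. The effect of movable cut-offs has not been quantified. This is a worthwhile improvement to a secondary part of the plan, not a threat to its main inference.

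**What to change.** In SAP section 4.9.1.4:

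1. Replace the within-level p-values with the treatment difference and its 95% CI per level, and put these on the forest plot.
2. Add one treatment-by-subgroup interaction or homogeneity test per factor, using an exact or risk-difference method where placebo responders are sparse.
3. State that these tests are descriptive, unadjusted for multiplicity and low-powered.
4. Fix the factors, the cut-offs and any rule for merging sparse levels before Part 2 is unblinded, and label later changes post hoc.

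The cost is SAP wording and a modest amount of extra analysis. No new data and no change to trial conduct are needed. The drawback is that a non-significant interaction test will say little, and the text should admit this.
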